9.3.2. Pharmacokinetic Analyses

9.3.2.1. Pharmacokinetic Parameter Estimation

Pharmacokinetic parameter estimates for plasma total radioactivity, plasma LY3484356, and plasma [¹⁴C]-LY3484356 will be calculated by standard noncompartmental methods. The primary PK parameters for analysis will be: AUC(0-∞) and C_{max}.

Other noncompartmental parameters, such as t_{max}, t_{1/2}, apparent total body clearance of drug calculated after extravascular administration (CL/F), apparent volume of distribution during the terminal phase after extravascular administration (Vz/F), and volume of distribution at steady state (V_{dss}), may be reported as appropriate. In Part 2, the absolute bioavailability (F) of LY3484356 will also be calculated.

The plasma:total radioactivity ratio of LY3484356 will be calculated for each time point. The percent of radiolabeled dose recovered in feces, urine, and expired air will be calculated in Part 1.

The following PK parameters will be determined from urinary concentrations of total radioactivity: amount of drug excreted in urine (A_e), cumulative A_e, percentage of dose excreted in urine (f_e), cumulative f_e. Renal clearance (CLR) will also be determined for [¹⁴C]-LY3484356 only.

The following PK parameters will be determined from fecal concentrations of total radioactivity: amount of drug excreted in feces (A_{ef}), cumulative A_{ef}, percentage of dose excreted in feces (f_{ef}), and cumulative f_{ef}.

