3. INTRODUCTION

This SAP has been developed after review of the Clinical Study Protocol (final version dated 25 May 2021), and Protocol Amendment (a) (final version dated 25 June 2021).

This SAP describes the planned analysis of the safety, tolerability and pharmacokinetic (PK) data from this study. A detailed description of the planned TFLs to be presented in the clinical study report (CSR) is provided in the accompanying TFL shell document.

The intent of this document is to provide guidance for the statistical and PK analyses of data. In general, the analyses are based on information from the protocol, unless they have been modified by agreement with Eli Lilly and Company. A limited amount of information concerning this study (e.g., objectives, study design) is given to help the reader's interpretation. For open-label studies, this SAP must be signed off prior to first participant visit for this study. When the SAP and TFL shells are agreed upon and finalized, they will serve as the template for this study's CSR.

This SAP supersedes the statistical considerations identified in the protocol; where considerations are substantially different, they will be so identified. If additional analyses are required to supplement the planned analyses described in this SAP, they may be performed and will be identified in the CSR. Any substantial deviations from this SAP will be agreed upon with Eli Lilly and Company and identified in the CSR. Any minor deviations from the TFLs may not be documented in the CSR.

This SAP is written with consideration of the recommendations outlined in the International Conference on Harmonisation (ICH) E9 Guideline entitled Guidance for Industry: Statistical Principles for Clinical Trials¹ and the ICH E3 Guideline entitled Guidance for Industry: Structure and Content of Clinical Study Reports².

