9. STATISTICAL METHODOLOGY

9.1 General

Data listings will be provided for all data that is databased. Summary statistics and statistical analysis will only be presented for data where detailed in this SAP. For continuous data, summary statistics will include the arithmetic mean, arithmetic standard deviation (SD), median, minimum, maximum and n; for log-normal data (e.g. the PK parameters: area under the concentration versus time curve [AUC] and C_{max}) the geometric mean and geometric coefficient of variation (CV%) will also be presented. For categorical data, frequency count and percentages will be presented. Data listings will be provided for all participants up to the point of withdrawal, with any participants excluded from the relevant population highlighted. Summary statistics and statistical analyses will generally only be performed for participants included in the relevant analysis population. For the calculation of summary statistics and statistical analysis, unrounded data will be used.

Mean change from baseline is the mean of all individual participants’ change from baseline values. Each individual change from baseline will be calculated by subtracting the individual participant’s baseline value from the value at the timepoint. The individual participant’s change from baseline values will be used to calculate the mean change from baseline using a SAS procedure such as Proc Univariate.

Data analysis will be performed using SAS[®] Version 9.4 or greater.

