Additional PK parameters may be calculated, as appropriate. The PK excretion data will be presented in the radioanalysis report.

The percentage and cumulative percentage of radiolabeled dose excreted in expired air may also be presented for Part 1, if applicable.

The software and version used for the final analyses will be specified in the CSR. Any exceptions or special handling of data will be clearly documented within the final CSR.

Formatting of tables, figures and abbreviations will follow the Eli Lilly Global PK/PD/TS Tool: NON-COMPARTMENTAL PHARMACOKINETIC STYLE GUIDE. The version of the tool effective at the time of PK analysis will be followed.

General PK Parameter Rules

- Actual sampling times will be used in the final analyses of individual PK parameters, except for non-bolus pre-dose sampling times which will be set to zero. For non-bolus, multiple dose profiles, the pre-dose time will be set to zero unless a time deviation falls outside of the protocol blood collection time window which is considered to impact PK parameter derivation.
- The C_{max} and t_{max} will be reported from observed values. If C_{max} occurs at more than one timepoint, t_{max} will be assigned to the first occurrence of C_{max} .
- The AUC parameters will be calculated using a combination of the linear and logarithmic trapezoidal methods (linear-log trapezoidal rule). The linear trapezoidal method will be applied up to t_{max} and then the logarithmic trapezoidal method will be used after t_{max} . The minimum requirement for the calculation of AUC will be the inclusion of at least three consecutive plasma concentrations above the lower limit of quantification, with at least one of these concentrations following C_{max} .
- Any $AUC(0-\infty)$ values where the percentage of the total area extrapolated is more than 20% will be flagged. Any $AUC(0-\infty)$ value excluded from summary statistics will be noted in the footnote of the summary table.

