11. CHANGES FROM THE PROTOCOL SPECIFIED STATISTICAL ANALYSES

There were no changes from the protocol specified statistical analyses.

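### Does the SAP drop the renal clearance of [14C]-LY3484356 that the protocol says will be determined?

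*SAP*

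**What the plan says.** Protocol 9.3.2.1 treats its parameters with different firmness. Several plasma parameters (tmax, t1/2, CL/F, Vz/F and volume at steady state) "may be reported as appropriate". CLR stands in the urinary paragraph, directly after the amounts and percentages of dose excreted, and carries no condition: "Renal clearance (CLR) will also be determined for" [14C]-LY3484356 only.

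SAP 9.3.1 tabulates 13 parameters, all derived from plasma. CLR is not among them. After the table come two general sentences: "Additional PK parameters may be calculated, as appropriate" and "The PK excretion data will be presented in the radioanalysis report".

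Three other SAP statements bear on the question:

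- Section 9.1: "Summary statistics and statistical analysis will only be presented for data where detailed in this SAP".
- Section 3: the SAP takes precedence over the protocol's statistical text, and "where considerations are substantially different, they will be so identified". It also says "If additional analyses are required to supplement the planned analyses described in this SAP, they may be performed", with such analyses identified in the study report.
- Section 11: "There were no changes from the protocol specified statistical analyses".

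**The concern.** Every parameter that the protocol left optional reached the SAP table, while a parameter that it stated firmly did not. CLR divides a urinary amount by a plasma AUC. The first belongs with the excretion data sent to the radioanalysis report and the second with the SAP's own PK analysis, so CLR could fall between the two. Read strictly, SAP 9.1 would then keep it out of the summary tables, and section 11 would be wrong to report no departure from the protocol.

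The stake would be interpretive. The protocol's rationale for Part 1 includes judging whether renal impairment is likely to affect the drug's disposition, and CLR of the parent speaks to that directly. If CLR first appeared as an unplanned addition, a reader might ask whether its definition had been settled after the data were seen.

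**Working it through.** **Side-by-side reading**

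| Item in Protocol 9.3.2.1 | Protocol | SAP 9.3.1 |
|---|---|---|
| AUC(0-∞), Cmax, F | firm | in the table |
| tmax, t1/2, CL/F, Vz/F, Vss | optional | in the table |
| Urinary and fecal amounts and percentages of dose | firm | not named; covered by the sentence on excretion data |
| Percentage of dose in expired air | firm | named, but only as something that may be presented |
| CLR | firm | not named |

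Two things follow. First, a firm protocol item that the SAP does not list one by one is not thereby dropped. The urinary and fecal percentages are the Part 1 primary endpoint, and SAP 9.3.1 handles them only through the pointer to the radioanalysis report. Second, a permissive verb in the SAP does not by itself signal a change, because expired air is handled that way too. Expired air is at least named, and CLR is not, so the parallel is incomplete.

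**Can CLR be derived from what is planned?**

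CLR = (unchanged [14C]-LY3484356 excreted in urine) / (plasma AUC of [14C]-LY3484356)

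- *Analyte:* fixed by Protocol 9.3.2.1.
- *Numerator:* Protocol 4.2 foresees the amount of drug excreted unchanged in urine, from urine concentrations of [14C]-LY3484356. Protocol 8.6 plans drug concentrations in an aliquot of each urine sample, with urine collection described for Part 1. Section 8.6 uses the unlabelled name. Since the only Part 1 dose is drug containing the labelled form, this is most simply loose naming. Nothing in either document puts total radioactivity in the numerator.
- *Denominator:* Protocol 8.6.1 quantifies plasma [14C]-LY3484356 in Part 1, and SAP 9.3.1 derives AUC(0-tlast) and AUC(0-∞) for it. The SAP's restriction to Part 2 applies to plasma LY3484356, not to the labelled analyte.

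**How much freedom is left?** The open choice is AUC(0-∞) or AUC over the urine collection interval. Inputs:

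- Half-life of 25 to 30 h (Protocol 2.2.2, cancer patients; assumed to hold here).
- Earliest discharge on Day 12 (Protocol 4.1.2), that is 11 × 24 = 264 h after dosing.

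Share of AUC(0-∞) lying after 264 h, with a single exponential:

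- 25 h: 2^(−264/25) = 0.00066, or 0.07%
- 30 h: 2^(−264/30) = 0.00224, or 0.22%

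With the same urinary amount, the interval AUC gives a CLR larger by a factor of at most 1/(1 − 0.00224) = 1.0022. Later discharge makes the difference smaller. The plasma sampling times are redacted, so it cannot be confirmed that plasma sampling matches the urine interval.

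**What depends on CLR?** It appears in no objective or endpoint table in either document. The Part 1 primary endpoint is excretion of total radioactivity and the Part 2 primary endpoint is F; neither uses it. Urinary total radioactivity is also an upper bound on unchanged parent in urine, so the endpoint already limits how important renal clearance of the parent can be. CLR adds information only if that bound is appreciable.

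**The case for a change.** The strongest argument for a change is that the protocol says CLR will be determined, and the SAP, which takes precedence, only permits additional parameters. Permission is not a commitment. The excretion sentence does not clearly reach CLR either, because half of the ratio is a plasma quantity. If the radioanalysis report is the intended place, one sentence would have said so, and the cost is trivial.

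Part of this stands: the SAP does not name CLR, give its formula, or say who combines the two inputs and where the result appears.

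The heavier charges do not stand:

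- **SAP 9.1.** Applied literally, its limit on summaries would also bar the excretion percentages, which are the Part 1 primary endpoint and are plainly meant to be reported elsewhere.
- **SAP section 11.** It speaks of statistical analyses, and both documents plan no formal statistical analysis of PK (Protocol 9.3.3, SAP 9.3.2). Section 3 asks only that substantial differences be identified. An unlisted descriptive parameter that is not an endpoint is hard to call substantial, and silence is not a decision to omit it.
- **Choice after seeing the data.** The analyte is already fixed, and the remaining AUC choice is worth about 0.2% at most on the stated assumptions.

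**Conclusion.** The observation is accurate, but no change to the plan follows. It is a gap in detail that a PK analyst holding both documents would fill correctly: the protocol's commitment remains, the SAP permits the calculation, the inputs are planned, and the formula is standard. No stated rule produces a wrong result. The effect on primary and secondary endpoints is nil, and the residual ambiguity in CLR itself is about 0.07% to 0.22%. The cost of leaving the text alone is a small loss of traceability.

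This rests on three assumptions: the patient half-life is a fair guide for these healthy women; the urinary measurement of unchanged drug is made as Protocol 4.2 and 8.6 describe; and plasma sampling supports the AUC. The TFL shells and the radioanalysis report are not among the documents, so whether either already provides for CLR cannot be checked. The conclusion does not depend on that.

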- The average plasma concentration profiles will be graphed using arithmetic average concentrations.
- The pre-dose average plasma concentration for single-dose data from non-endogenous compounds will be set to zero. Otherwise, only quantifiable concentrations will be used to calculate average concentrations.

- Plasma concentrations at a sampling time exceeding the sampling time window specified in the protocol, or $\pm 10\%$, will be excluded from the average concentration profiles.
- Concentrations excluded from the mean calculation will be documented in the final CSR.
- A plasma concentration average will be plotted for a given sampling time only if 2/3 of the individual data at the time point have quantifiable measurements that are within the sampling time window specified in the protocol or $\pm 10\%$. An average concentration estimated with less than 2/3 but more than 3 data points may be displayed on the mean concentration plot if determined to be appropriate and will be documented within the final CSR.

Treatment of Outliers during Pharmacokinetic Analysis

Application of this procedure to all PK analyses is not a requirement. Rather, this procedure provides justification for exclusion of data when scientifically appropriate. This procedure describes the methodology for identifying an individual value as an outlier for potential exclusion, but does not require that the value be excluded from analysis. The following methodology will not be used to exclude complete profiles from analysis.

Data within an Individual Profile

A value within an individual profile may be excluded from analysis if any of the following criteria are met:

- For PK profiles during multiple dosing, the concentration of the pre-dose sample exceeds all measured concentrations for that individual in the subsequent post-dose samples.
- For PK profiles during single dosing of non-endogenous compounds, the concentration in a pre-dose sample is quantifiable.
- For any questionable datum that does not satisfy the above criteria, the profile will be evaluated and results reported with and without the suspected datum.

Data between Individual Profiles

1. If $n < 6$, then the dataset is too small to conduct a reliable range test. Data will be analyzed with and without the atypical value, and both sets of results will be reported.
2. If $n \geq 6$, then an objective outlier test will be used to compare the atypical value to other values included in that calculation:

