 - a. Transform all values in the calculation to the logarithmic domain.
 - b. Find the most extreme value from the arithmetic mean of the log transformed values and exclude that value from the dataset.
 - c. Calculate the lower and upper bounds of the range defined by the arithmetic mean $\pm 3 \times \text{SD}$ of the remaining log-transformed values.

- d. If the extreme value is within the range of arithmetic mean $\pm 3*SD$, then it is not an outlier and will be retained in the dataset.
- e. If the extreme value is outside the range of arithmetic mean $\pm 3*SD$, then it is an outlier and will be excluded from analysis.

If the remaining dataset contains another atypical datum suspected to be an outlier and $n \geq 6$ following the exclusion, then repeat step 2 above. This evaluation may be repeated as many times as necessary, excluding only one suspected outlier in each iteration, until all data remaining in the dataset fall within the range of arithmetic mean $\pm 3*SD$ of the log-transformed values.

Reporting of Excluded Values

Individual values excluded as outliers will be documented in the final CSR. Approval of the final report will connote approval of the exclusion.

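### At 6 to 8 participants the 3-SD outlier rule, applied as written, removes a genuine value from up to about a quarter to a third of clean datasets, with no all-data result required

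*SAP*

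**What the plan says.** The outlier procedure is in SAP section 9.3.1, under Treatment of Outliers during Pharmacokinetic Analysis. Its opening paragraph makes it discretionary: "Application of this procedure to all PK analyses is not a requirement", and the method "does not require that the value be excluded from analysis".

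For comparisons between participants there are two branches.

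- **n below 6.** The SAP considers the dataset too small for a reliable range test. "Data will be analyzed with and without the atypical value, and both sets of results will be reported".
- **n of 6 or more.** Values are logged, the one farthest from the mean is set aside, and the mean and SD of the remaining n−1 are calculated. If the value set aside is more than 3 SD from that mean, "then it is an outlier and will be excluded from analysis". While n is still at least 6, "This evaluation may be repeated as many times as necessary, excluding only one suspected outlier in each iteration".

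For a questionable value within one participant's profile that meets none of the listed exclusion criteria, "the profile will be evaluated and results reported with and without the suspected datum".

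On disclosure, "Individual values excluded as outliers will be documented in the final CSR", and approval of the final report counts as approval of the exclusion. Section 9.1 says that for log-normal parameters such as AUC and Cmax "the geometric mean and geometric coefficient of variation (CV%) will also be presented". Section 7 plans at least 6 evaluable participants from up to 8 enrolled in Part 2, and at least 4 from up to 6 in Part 1.

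**The concern.** Three things combine.

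1. The opening paragraph leaves exclusion to judgement, while step 2e makes it automatic. The SAP does not say which governs, so two analysts could report different n, geometric mean and CV from the same data.
2. The duty to show both results ends at n=6, where Part 2 begins. It also ends there for Part 1 plasma parameters if all 6 participants are evaluable. Part 1 excretion data go to the radioanalysis report and are outside this point.
3. The 3-SD limit looks strict but is not. The test picks the most extreme of n values, then judges it against an SD from which it has been removed and which rests on only 5 to 7 values.

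No formal inference is planned, so the geometric mean and geometric CV are the main Part 2 results. A rule that trims genuine values makes F look more consistent between participants than it is, and makes its geometric mean less precise.

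**Working it through.** The SAP gives no error rate for the rule, so there is no figure of its own to reproduce.

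**Inputs.** From SAP 9.3.1: log scale, most extreme value set aside, limit of 3 SD of the other n−1, repeat allowed while n is at least 6. From SAP 7: n = 6, 7, 8. Assumption: clean log-normal data, which SAP 9.1 takes for AUC and Cmax but does not state for F. The removal rate does not depend on the true mean or CV.

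**Exact calculation.** For a clean value x, with m and s the mean and SD of the other n−1 log values,

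(x − m) / (s·√(n/(n−1))) follows a t distribution with n−2 df.

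The 3-SD limit is therefore a t cut-off of 3/√(n/(n−1)). With p the two-sided tail beyond it, n·p bounds the chance that any value is removed. The simulated column applies steps 2a to 2e as written to 2,000,000 datasets per n.

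| n | t cut-off | df | p per value | n·p | Simulated |
|---|---|---|---|---|---|
| 6 | 2.739 | 4 | 0.0520 | 31.2% | 31.2% |
| 7 | 2.777 | 5 | 0.0390 | 27.3% | 27.3% |
| 8 | 2.806 | 6 | 0.0309 | 24.7% | 24.7% |

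For comparison, at n=5, which the SAP calls too small, the cut-off is 3/√(5/4) = 2.683 on 3 df, p = 0.0748 and n·p = 37.4%. The step from 5 to 6 lowers the rate only to 31.2%, yet the wording changes from reporting both results to exclusion.

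**Effect on what is reported, one pass.** CV = √(exp(s²) − 1), with an assumed true CV of 30%.

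| | n=6 | n=7 | n=8 |
|---|---|---|---|
| Mean log-SD (true SD 1), before → after | 0.951 → 0.813 | 0.960 → 0.849 | 0.965 → 0.873 |
| Fall in mean log-SD | 15% | 12% | 10% |
| Mean CV, all datasets | 28.7% → 24.4% | 28.9% → 25.5% | 29.1% → 26.2% |
| Median SD ratio where a value is removed | 0.56 | 0.60 | 0.64 |
| Rise in variance of the log mean | 24% | 20% | 17% |
| Rise in its standard error | 11% | 9% | 8% |

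In datasets that lose a value, the median CV goes from 27.9% to 14.5% (n=6) or from 28.5% to 17.2% (n=8). The geometric mean moves by a median of 10% (n=6) or 8% (n=8). Over true CVs of 20% to 50%, that move is 7% to 17% (n=6) and 6% to 14% (n=8). It can go either way, and on average over datasets there is no bias.

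**Repeat passes.** Two or more genuine values are lost in 8.5% (n=7) or 6.7% (n=8) of clean datasets. At n=6 no second pass is allowed.

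**If F is not log-normal.** With raw-scale normal (CV 10% to 30%), logit-normal, beta and uniform shapes, the one-pass rate was 26% to 39% (n=6), 21% to 37% (n=7) and 18% to 36% (n=8). These ranges belong to the shapes tried and are not limits.

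**The case against.** The strongest reply is that the SAP does not prescribe what was calculated. The procedure is optional, is meant for cases where exclusion is scientifically justified, and starts from a value already judged atypical. On that reading the opening paragraph governs, and step 2e only describes the outcome once discretion has been used. This stands as far as the rates go: they are ceilings, and the realised rate would be lower and cannot be derived from the documents. It does not settle the wording, because the SAP never says the opening paragraph overrides 2e. A value beyond 3 leave-one-out SD is also the kind likely to look atypical. Deciding whether to test after seeing open-label data is a reason to show both results.

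A second reply is that the SAP is consistent: where an objective criterion is met, exclude and document; where none is available, report both. That describes the pattern fairly, including within profiles. However, a criterion that clean data meet this often at n=6 to 8 cannot carry that weight.

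Third, exclusions are disclosed. They are documented in the CSR, excluded AUC(0-∞) and half-life values are footnoted, and individual data are listed. Nothing is hidden, and a reader could rebuild the full summary. The sponsor is still not required to present it. The table shells are a separate document and were not available.

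Fourth, the procedure may not be used to remove complete profiles, which might be thought to protect F. One participant's F is a single derived value, not a concentration profile, so that sentence does not clearly cover it.

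Finally, no test or decision depends on the SD. True, but the descriptive summary is then the result itself.

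**Conclusion.** The point holds. Step 2e conflicts with the opening paragraph, and the requirement to report both results is missing at every planned Part 2 size. Followed literally on every dataset, the rule removes a genuine value from up to 31.2%, 27.3% and 24.7% of clean log-normal datasets at n=6, 7 and 8, and lowers the average log-SD by 15%, 12% and 10%. The rates assume log-normal data and that every flag is acted on; the CV figures also assume a true CV of 30%. The harm is understated spread and lost precision, not bias in the geometric mean and not concealment. It should be fixed because it bears on the primary Part 2 result.

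**What to change.** Make two changes in SAP section 9.3.1.

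1. In step 2e, replace the mandatory exclusion with wording such as *is flagged for potential exclusion*, in line with the opening paragraph.
2. Extend the reporting sentence for n below 6 to every n: give results with and without the flagged value, and name the all-data result as the main one. The present n<6 rule ranks neither result, so naming the main one is an addition. It prevents the choice from being made after the data are seen.

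Changing the multiplier is optional once both results are shown. For reference, a 5% chance per clean dataset of removing any value would need about 5.31 SD (n=6), 4.73 SD (n=7) or 4.40 SD (n=8), using a Bonferroni bound.

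The cost is two sentences and at most one extra summary table. The main reported CV may be larger.
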